Obesity is strongly linked to systemic inflammation with increased circulating pro-inflammatory cytokines and adipokines and elevated C-reactive protein (CRP) reported in obese children as young as age three¹⁰⁻¹⁵. Examining NHANES data from over sixteen thousand children, Skinner et al¹⁵ found that prevalence of C-reactive protein (CRP) levels >1mg/L was greater in very obese children beginning at age 3 and continued through adolescence, with greater than 80% of very obese adolescents having CRP >1mg/L as compared to 18% of lean adolescents. While the dataset did not permit controlling for pubertal age, similar results were found even when very narrow age groups were compared. In a smaller study of children ages 7-14 years, Codoner-Franch et al¹⁶ classified obese children as metabolically healthy or at risk based on well-defined criteria, and they reported CRP, Tumor necrosis factor α (TNF α) and Interleukin (IL) 6 were all increased in obese children with or without metabolic risk factors, suggesting that inflammation may appear early in obesity before metabolic alterations. Inflammation is considered pivotal to the development of obesity-related metabolic disorders including insulin resistance, T2D¹⁷⁻¹⁹ and cardiovascular dysfunction^{20, 21}. Modulation of inflammation in obese children provides a putative “target” for therapeutic intervention.

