to complete the procedure(s). At the first, second, or reattempt visits, participants/parents may be given up to \$20 in ACRI merchandise and/or child-friendly stickers. Food and drinks may be provided during study visits following the fasting blood draw.

Study Population

110 children ages 5-17 years old will be recruited with the goal that approximately 80 subjects stratified across the following groups will complete the study: i) healthy lean (approximately n=20); ii) overweight/obese (approximately n=40, with the anticipation that approximately 20 of these children will be insulin resistant); iii) overweight/obese with T2D and prescribed Metformin (approximately n=20). Every attempt will be made to ensure that the desired number for each group is achieved and groups are balanced with respect to age, sex and ethnicity.

Inclusion Criteria:

- Age 5-17 years, inclusive
- Either healthy lean ($BMI \geq 5^{\text{th}}$ percentile and $< 85^{\text{th}}$ percentile for age/sex) or overweight ($BMI \geq 85^{\text{th}}$ percentile and $< 95^{\text{th}}$) or obese ($BMI \geq 95^{\text{th}}$ percentile for age/sex)
- For those with $BMI \geq 85^{\text{th}}$ percentile for age/sex, parental verbal confirmation that the child had a history of $BMI \geq 85^{\text{th}}$ percentile for age/sex for at least six months prior to study enrollment

OR

- Age 5 years - 17 years 5 months, inclusive
- Either overweight or obese ($BMI \geq 85^{\text{th}}$ percentile for age/sex)
- Parental verbal confirmation that the child had a history of $BMI \geq 85^{\text{th}}$ percentile for age/sex for at least six months prior to study enrollment
- Diagnosed with type 2 diabetes mellitus or insulin resistance
- Prescribed metformin (either not yet taking or began taking within 3 weeks of enrollment)

Exclusion criteria:

- Having an infection (viral, respiratory, gastrointestinal) in the previous 4 weeks
- Genetic or physical conditions impacting mobility over past year as determined by the PI
- Having known chronic illnesses/disorders that may independently affect study outcome measures: type 1 diabetes mellitus, neurologic (e.g. epilepsy), developmental (developmental delay, autism spectrum disorder), endocrine (thyroid, Cushing's), hepatic, autoimmune, cardiac and renal disorders. Also, chronic lung disorders except well controlled asthma that does not require permanent use of inhaled/oral steroids

Title: Immunometabolism in Pediatric Obesity

PI: [name].

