Prior to any analyses, endpoints data for each group will be closely inspected for the potential presence of unusual values; effort will be made to conserve all data. Analyses will be carried out in SAS 9.4 (SAS Institute, Cary NC) at the 5% significance level; point and 95% interval estimates will be obtained for relevant metabolic group comparisons. Parametric techniques will be first choice and nonparametric equivalents if assumptions are not met. Special attention will be paid to unequal variances.

The study planned four groups of children: lean, healthy obese/overweight, insulin-resistant obese/overweight, and overweight/obese with T2D. Primary comparison of interest are these three: the average of insulin-resistant and T2D obese children compared to (i) lean children and (ii) healthy obese children; and (iii) lean children compared to healthy obese children. Outcomes important to this aim are proportions of T_{reg} cells among circulating CD4 $^{+}$ T cells and CD4 $^{+}$ T glycoATP and mitoATP production. Initially, we will use a one-factor ANOVA to analyze these outcomes (possibly with suitable transformations). Comparisons of interest will then be made with 0.05 significance level *t*-tests conducted within the ANOVA framework.

The requested sample sizes will provide about 0.80 power for detecting differences in means of size 0.8 SD for comparisons (i) and (ii) and size 0.9 SD for comparison (iii), where SD is the within-group standard deviation (a.k.a., root mean square error from the ANOVA). For proportions of T_{reg} cells – a primary outcome of interest, an estimate of the SD is 2.3 percentage points (ref Table 1 of Arismendi et al.⁴²). So, if the means differ by at least 1.85 percentage points in comparisons (i) & (ii) and by 2.10 percentage points for comparison (iii), we will be able to detect these differences with a reasonably high probability (0.80 or higher).

Ethical Considerations

This study will be conducted in accordance with all applicable government regulations and University of Arkansas for Medical Sciences research policies and procedures. This protocol and any amendments will be submitted and approved by the UAMS Institutional Review Board (IRB) to conduct the study.

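### Comparison (ii) can mix degree of adiposity with metabolic status, because the overweight/obese groups are neither balanced nor adjusted for it

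*Combined protocol and SAP*

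**What the plan says.** The Data Analysis section plans four groups and three primary comparisons. Two of them are "the average of insulin-resistant and T2D obese children compared to (i) lean children and (ii) healthy obese children"; the third is lean against healthy overweight/obese children. The outcomes are the Treg proportion and glycolytic and mitochondrial ATP production in CD4+ T cells. The first analysis is a one-factor ANOVA, and no covariate is named. "Comparisons of interest will then be made with 0.05 significance level" t-tests within that model.

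Study Population sets the groups: about 20 lean; "overweight/obese (approximately n=40, with the anticipation that approximately 20 of these children will be insulin resistant"; and about 20 with T2D. All heavy children enter at or above the 85th BMI percentile, overweight and obese together, with no upper limit. The recruitment aim is that "groups are balanced with respect to age, sex and ethnicity". Preliminary Data says that heavy children will be subdivided by insulin sensitivity.

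In the list of study procedures, height, weight, waist and hip are to be measured, and bioimpedance may be. BMI-for-age is used to confirm the lean/obese stratum. No adiposity measure is given a role in the analysis.

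**The concern.** Comparison (ii) sets heavy children with metabolic dysfunction against heavy children without it, so the natural reading of a difference is that metabolic status explains it. Preliminary Data already reads a T2D-versus-obese difference that way. The reading needs the two sides to be similar in adiposity, and nothing in the recruitment plan or the model secures that.

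The protocol gives grounds for treating adiposity as a possible cause of the outcomes in its own right. The background cites fewer circulating Tregs in obese adults. It also cites raised inflammatory markers in obese children whether or not they had metabolic risk factors, and a higher prevalence of raised CRP in very obese children. The procedures section applies the same logic elsewhere: pubertal stage has to be accounted for, and depression is measured as a confounder. Adiposity gets no such statement.

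At stake is the interpretation of one of the three primary comparisons. A difference could be reported as a feature of insulin resistance and T2D when part of it is a feature of being heavier.

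**Working it through.** **Inputs from the documents.** About 20 children per group in four groups; 0.05 per comparison (two-sided assumed, since sidedness is not stated); stated power of about 0.80 at 0.8 SD for (i) and (ii) and at 0.9 SD for (iii); for the Treg proportion, "an estimate of the SD is 2.3 percentage points".

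**The plan's own power figure.** Residual df = 80 − 4 = 76.
- (i) and (ii): SE = SD × √[(1/4)(1/20 + 1/20) + 1/20] = SD × √0.075 = 0.274 SD. Noncentral t power at 0.8 SD is 0.822.
- (iii): SE = SD × √(2/20) = 0.316 SD. Power at 0.9 SD is 0.802.
- In percentage points: 0.8 × 2.3 = 1.84 (stated 1.85) and 0.9 × 2.3 = 2.07 (stated 2.10).

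The stated power is reproduced. It takes comparison (ii) to be free of confounding.

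**Illustration of bias in (ii).** Assume no metabolic effect at a given adiposity, and an unchanged within-group SD. Let the share of overweight (not obese) children differ between the two sides by p, and let overweight and obese children differ by d SD on the outcome. The spurious difference is p × d. The rejection rate comes from the noncentral t with 76 df and noncentrality p × d / 0.274. The documents give neither p nor d.

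| p | d (SD) | Spurious difference (SD) | Treg points (× 2.3) | Rejection rate |
|---|---|---|---|---|
| 0.20 | 0.3 | 0.06 | 0.14 | 5.5% |
| 0.40 | 0.5 | 0.20 | 0.46 | 11.1% |
| 0.60 | 0.8 | 0.48 | 1.10 | 40.9% |

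A continuous version gives a similar range. With an adiposity imbalance of D SD and a within-group correlation r between adiposity and outcome, the spurious difference is r × D. Over D from 0.25 to 1.0 and r from 0.1 to 0.5, the rejection rate runs from 5.1% to 43.8%; at D = 0.5 and r = 0.3 it is 8.4%.

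**Cost of adjustment.** With one adiposity covariate, SE² = (1 − r²)(0.075 + D²/S) in SD² units, where S is the within-group sum of squares of adiposity in SD units. With a slope common to all four groups, S = 76 and df = 75. With the 60 heavy children only, S = 57 and df = 60 − 3 − 1 = 56. Power for a true 0.8 SD difference:

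| D | r | Four groups, common slope | Heavy children only |
|---|---|---|---|
| 0.5 | 0.3 | 0.84 | 0.83 |
| 1.0 | 0.1 | 0.76 | 0.74 |
| 1.5 | 0.1 | 0.69 | 0.65 |

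The unadjusted contrast without imbalance has 0.82.

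**The case against.** The purpose of comparison (ii) is inferred: no sentence says that it isolates metabolic dysfunction, and Aim 1 is framed as lean against overweight/obese. The study is observational and meant to supply preliminary data. The ANOVA is described only as the initial analysis, which leaves room for later models. These points limit the severity. They do not remove the gap, because no covariate is named and the healthy/insulin-resistant split has little use unless (ii) is read as a metabolic contrast.

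The evidence on adiposity is also indirect. A reader might take "greater than 80% of very obese adolescents having CRP >1mg/L as compared to 18% of lean adolescents" as the size of the problem. It is not: it compares very obese with lean adolescents, says nothing about overweight against obese, and concerns CRP rather than Tregs or ATP production. The preliminary bioenergetic data showed no lean–obese difference, although in mixed PBMC with 8 and 11 children.

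A reader might also infer that the insulin-resistant/T2D side will be the heavier one. That is plausible, but no passage states it. Nor should the short label for the healthy group be read as a claim that all its children are obese: the same section first defines that group as including overweight children.

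Finally, adjustment is not free. If adiposity and metabolic status are closely tied, the adjusted contrast is imprecise, and its failure to reach significance would settle nothing. That objection stands and shapes the fix.

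**Conclusion.** The gap is real and inexpensive to close. As planned, comparison (ii) cannot separate metabolic status from degree of adiposity, and nothing elsewhere in the documents supplies that separation. What is established is that the two sides can differ in adiposity without the design or model taking account of it. Whether they will, in which direction and by how much is not established.

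The range of 5.5% to 41% therefore shows what could happen under assumed inputs; it is not an estimate of this study's error rate. The low end is practically nominal. The high end needs a 0.8 SD gap between overweight and obese children, close to the 0.9 SD for which comparison (iii) is powered. The calculation also assumes the planned group sizes, equal variances and two-sided testing. The plan's power arithmetic is sound on its own inputs and is not in question.

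**What to change.** In Data Analysis, keep the unadjusted comparison (ii) and prespecify beside it an ANCOVA contrast adjusted for one continuous BMI-severity measure from visit 1, for example BMI as a percentage of the 95th percentile. Estimate the slope among the overweight/obese children, so that lean children do not determine it. BMI is preferable to body-fat percentage because bioimpedance is optional. Report BMI by group.

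State how the two results will be read. Give both estimates with 95% intervals. Do not attribute an unadjusted difference to metabolic status independent of adiposity without showing the adjusted estimate. Do not treat loss of significance after adjustment as evidence of no metabolic effect.

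Balancing enrolment by BMI class is not a substitute. Insulin and glucose come from the study blood sample, so metabolic status may be unknown at enrolment, and class does not balance the open-ended obese range.

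The cost is a few sentences of analysis text, with no new measurement. Precision changes little at moderate imbalance (power 0.83 at D = 0.5 and r = 0.3 in the heavy-only model) and falls further where adiposity and metabolic status are strongly linked (0.74 at D = 1.0 and r = 0.1).

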treatment in pre-diabetic adults reduced mTOR activity in PBMC despite increases at the gene expression level; however, AMPK activity was not changed by metformin. Metformin's potential to induce T_{regs} has otherwise not been studied in obese individuals. We will take advantage of the fact that this AMPK activator is commonly prescribed in pediatrics and compare the immune and metabolic phenotypes of CD4⁺ T in obese insulin resistant/T2D children before and after metformin treatment. As such, we will explore whether a potential mechanism of action of metformin is via direct modulation of CD4⁺T cell metabolism, induction of T_{regs}, and curbing inflammation.

The main purpose of this proposed study is to determine whether the immunometabolic phenotypes of CD4⁺T cells from obese children is skewed towards T_{eff} with mTOR-driven glycolysis and away from T_{regs} with AMPK-driven OXPHOS and whether metformin can reverse the immunometabolic phenotypes. These studies are imperative to begin testing and implementing strategies targeting the AMPK and mTOR pathways to combat obesity-associated inflammation and prevent progression into serious health complications. This translational research will move the field forward in several ways. First, we will gain insight into the pathophysiology of obesity-associated inflammation and the progression into insulin resistance and T2D. Second, we have the opportunity to uncover novel therapeutic avenues for obesity-associate inflammation and prevention of metabolic dysfunction that target immune cell metabolism. Third, we may identify an immunometabolic phenotype that correlates to risk for developing T2D and/or cardiovascular dysfunction and could be used to monitor treatment response in future treatment trials. The findings from this study will form the preliminary data for a planned R01 application to the NIDDK to be submitted in Year 2. The goal of that proposal will be to conduct additional translational studies to expand upon this study and begin testing the ability to modifying bioenergetic control pathways to combat obesity-associated inflammation.

Preliminary Data

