In a current study (UAMS IRB #206164; Co-I: [name]), we have enrolled lean and obese subjects in a very narrow age range (5-9 years of age) in order to control for pubertal state. Bioenergetic profiling using the Seahorse XF96 Analyzer (Seahorse Bioscience, Inc., North Billerica, MA), a core ACRI equipment, is routinely performed by [name]⁻⁴⁰. The Seahorse measures oxygen consumption rate (OCR) and extracellular acidification rate (ECAR) in a 96-well plate of intact living cells. The sequential injection of up to four compounds into each well enables the interrogation of bioenergetics in real-time. **Figure 2A and B** presents the ATP Production Rate Assay on PBMC from lean, obese and T2D children enrolled in an ongoing study (UAMS IRB #206164; Co-I: [name]). In this assay, basal OCR and ECAR are initially measured, followed by the injection of oligomycin (oligo), an ATP synthase inhibitor, to block ATP production by the mitochondrial electron transport chain (ETC) and induce compensatory glycolysis. Next, antimycin A (AMA) and rotenone (ROT), inhibitors of ETC complex III & I, respectively, are injected together. Shutting down the ETC allows for calculating the amount of media acidification (ECAR) that was due to CO₂ production during OXPHOS. Proton efflux rate (PER) is calculated post-assay from ECAR and the buffering capacity of the assay media, and finally, validated calculations derive ATP generated by OXPHOS (mitoATP) and by glycolysis (glycoATP)⁴¹, which is presented in **Figure 2C**. **Figure 2D** shows that the % ATP derived from glycolysis is significantly greater in PBMC in the T2D group as compared to the OB group ($p=0.032$). While no differences between the lean and obese group are observed in this preliminary data, the increased % glycolysis in the T2D group supports the notion that obese children with metabolic dysfunction have more pro-inflammatory cells and fewer T_{regs} in circulation. There are several important points to

[figure not shown]

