Figure 2: The ATP production rate assay demonstrates increased % glycolysis-derived ATP production in PBMC from T2D children. Oxygen consumption rate (OCR) (A) and Proton Efflux Rate (PER) (B) are plotted over time in PBMCs from lean, obese (OB) and type 2 diabetic (T2D) children. Injections of Oligomycin (oligo) and Antimycin A (AMA) and Rotenone (ROT) are indicated. (C) Glycolytic ATP production rate (glycoATP) and mitochondrial ATP production rate (mitoATP) are calculated from OCR and PER. (D) % glycolysis and % OXPHOS-derived ATP production are calculated. * $p=0.032$

Methods: Freshly isolated PBMC from lean ($n=8$), obese (OB; $n=11$), and treatment-naive type 2 diabetic (T2D; $n=2$) children were plated at 2.5×10^6 cells/well in RPMI 1640 with 1mM HEPES, 2mM glutamine, 1mM pyruvate and 11mM glucose on poly-D-lysine coated XF96 plates. Plates were centrifuged at 100xg with no brake to adhere cells to well bottoms. After a 30 min incubation in a 37°C non-CO₂ incubator, cells were assayed in a Seahorse XF96.

note regarding this data: 1) these data are from PBMC, a mixed population of cells including monocytes and lymphocytes of various subtypes rather than purified CD4⁺ T cells as proposed in this study; 2) the obese subjects have not been classified as metabolically healthy or unhealthy; 3) the age of the T2D subjects is greater (16.5±0.1 years; mean±SD) than the other groups (lean: 6.8±1.1 years; obese: 7.9±1.4 years). In the studies proposed herein, we will match groups on age and subgroup obese subjects as metabolically healthy and unhealthy based on insulin sensitivity. Further, after measuring high sensitivity CRP (hsCRP), we will compare subjects with hsCRP values in the top quartile to the other groups to determine whether the % glycolysis is higher in CD4⁺T cells from those obese subjects with inflammation.

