OXPHOS/Glycolysis (OCR/ECAR; **Figure 3C**). These data demonstrate our ability to measure mTOR activation in small numbers of immune cells from children.

Hypothesis, Specific Aims, and Objectives

In this study, we hypothesize that compared to lean children, circulating CD4⁺T cells from obese children with elevated biomarkers of inflammation will have fewer T_{regs} and will exhibit increased mTOR-driven glycolysis. Metformin treatment will increase T_{regs} and shift the metabolic phenotypes of CD4⁺T cells towards AMPK-driven OXPHOS. We will test these hypotheses by executing the following Specific Aim:

Specific Aim 1. Compare the immune and metabolic phenotypes of circulating CD4⁺T cells between lean children and overweight/obese children.

Hypothesis: circulating CD4⁺T cells from obese children with elevated biomarkers of inflammation will have fewer T_{regs} and will exhibit increased mTOR activation and % glycolysis-derived ATP production as compared to CD4⁺T cells from lean children.

Specific Aim 2. Compare the immune and metabolic phenotypes of circulating CD4⁺T cells between T2D children before and after metformin.

Hypothesis: In obese T2D patients, metformin treatment will increase circulating T_{regs}, as well as AMPK activation and % OXPHOS-derived ATP production in CD4⁺ T cells.

Study Design and Procedures

This study consists of:

1. An observational cross sectional immune and metabolic analysis of several groups of children including lean, overweight/obese, and T2D.
2. A prospective immune and metabolic analysis of newly diagnosed children with T2D or insulin resistance who will be or were recently prescribed metformin as part of their clinical care.

Children with T2D or insulin resistance who will be or were recently prescribed metformin, will be asked to complete two study visits. If completed, the second visit will occur 6 months (+/- 2 weeks) after beginning metformin as part of their clinical care. All other children, will be asked to complete only the first visit.

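### Aim 1 predicts a higher percentage of ATP from glycolysis, but Data Analysis names only the glycoATP and mitoATP rates for comparisons (i)-(iii), and separate tests of two rates do not test the share

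*Combined protocol and SAP*

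**What the plan says.** **Hypothesis, Specific Aims, and Objectives.** The Aim 1 hypothesis is that CD4+ T cells from obese children with raised inflammatory markers "will exhibit increased mTOR activation and % glycolysis-derived ATP production as compared to" those from lean children. Aim 2 is also stated as a share: metformin is expected to raise Tregs "as well as AMPK activation and % OXPHOS-derived ATP production in" CD4+ T cells.

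**Background.** The main purpose is to find out whether the phenotype is "skewed towards T_{eff} with mTOR-driven glycolysis and away from T_{regs} with AMPK-driven OXPHOS", which describes a balance between two pathways.

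**Preliminary Data.** The legend to Figure 2 keeps the quantities apart. For panel C, "Glycolytic ATP production rate (glycoATP) and mitochondrial ATP production rate (mitoATP) are calculated from OCR and PER"; the percentages are a separate calculation in panel D. The supporting result is on the percentage: the text says Figure 2D "shows that the % ATP derived from glycolysis is significantly greater in PBMC in the T2D group as compared to the OB group" (p=0.032). This section also plans that, once hsCRP is measured, "we will compare subjects with hsCRP values in the top quartile to the other groups to determine whether the % glycolysis is higher" in CD4+ T cells from obese children with inflammation.

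**Data Analysis.** The outcomes listed for the one-factor ANOVA and comparisons (i)-(iii) are the Treg proportion and CD4+ "T glycoATP and mitoATP production. Initially, we will use a one-factor ANOVA to analyze these outcomes". The percentage is not named there. A clause allows suitable transformations of the listed outcomes.

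**The concern.** The prediction concerns where the ATP comes from, and the named tests concern how much each pathway makes. The two can part company in both directions:

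- If cells in one group simply make more ATP, both rates rise and both tests can reject although the split between pathways is unchanged.
- If the split changes but children differ widely in total output, that variation adds noise to each rate and both tests can miss the change.

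If Data Analysis is followed exactly, the bioenergetic part of Aim 1 has no matching prespecified test in (i)-(iii). A later analysis of % glycolysis across those groups would be hard to tell from a post hoc choice.

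**Working it through.** **Inputs from the documents.** Four groups of about 20 (Study Population: lean 20; overweight/obese 40, of whom about 20 insulin resistant; T2D 20). Contrasts, 0.05 level and target effects of 0.8 SD for (i) and (ii) and 0.9 SD for (iii) (Data Analysis). Sidedness is not stated; two-sided is assumed.

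**Step 1: the plan's own power.** Error df = 80 − 4 = 76.
- (i) and (ii), two groups averaged against one: variance factor 0.25 × (1/20 + 1/20) + 1/20 = 0.075. Noncentrality 0.8/√0.075 = 2.92, power 0.822.
- (iii): variance factor 1/20 + 1/20 = 0.10. Noncentrality 0.9/√0.10 = 2.85, power 0.802.

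Both agree with the stated figure of about 0.80. The same standardised power would apply to the share.

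**Step 2: why rates do not stand in for the share.** Let p be the glycolytic share and T total ATP, so glycoATP = pT and mitoATP = (1 − p)T. On the log scale:
- log glycoATP = log p + log T
- log mitoATP = log(1 − p) + log T
- log(glycoATP/mitoATP) = log[p/(1 − p)]

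T stays in each rate and cancels only in the ratio or the percentage. Transforming each rate separately does not remove it.

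**Step 3: assumed inputs.** The documents give an SD only for Tregs (2.3 percentage points). The following are assumptions: share 30%, SD 6 points (so 0.8 SD = 4.8 points), CV of total ATP 20% to 50%, share and total uncorrelated, rates analysed as logs.

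**Step 4: hand check, comparison (i), total ATP unchanged, CV 20%.** SD(log T) = √ln(1 + 0.20²) = 0.198.
- glycoATP: shift ln(34.8/30) = 0.148; SD ≈ √((6/30)² + 0.198²) = 0.281; effect 0.148/0.281 = 0.53 SD; power about 0.48.
- mitoATP: shift ln(65.2/70) = −0.071; SD ≈ √((6/70)² + 0.198²) = 0.216; effect 0.33 SD; power about 0.22.

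The share itself has an effect of 0.8 SD and power 0.82.

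**Step 5: simulation, comparison (i), 20,000 studies per setting.** The first figure in each cell is for CV 20%, the second for CV 50%.

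| True state | % glycolysis | glycoATP | mitoATP |
|---|---|---|---|
| 0.8 SD shift, total unchanged | 0.82 | 0.51, 0.19 | 0.23, 0.08 |
| 0.8 SD shift, mitoATP unchanged | 0.82 | 0.83, 0.35 | 0.05 |
| 0.8 SD shift, glycoATP unchanged | 0.82 | 0.05 | 0.96, 0.38 |
| No shift, total 20% higher | 0.05 | 0.62, 0.25 | 0.86, 0.28 |

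In the first row neither rate is significant in 34% (CV 20%) to 74% (CV 50%) of studies, against 18% missed on the share. In the last row both rates are significantly higher in 56% (CV 20%) to 18% (CV 50%). That is a true difference in output, not a type I error, but it is not the predicted shift.

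**Step 6: sensitivity.** Over 54 settings (share 20/30/50%, SD 4/6/10 points, CV 20/50%, share-total correlation −0.4/0/+0.4), the better of the two rate tests falls more than 0.02 below the share test in 52 with total ATP unchanged, 36 with mitoATP unchanged and 29 with glycoATP unchanged.

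**Step 7: a second parameterisation.** Lognormal rates, CV 30%, lean share about 35%, correlation between rates 0, 0.5 or 0.8.
- Both rates × 1.3: each rate rejects in about 89% of studies, the share in about 5%.
- glycoATP × 1.12 and mitoATP × 0.88: glycoATP rejects in 27-28%, mitoATP in about 34%, the share in 55%, 84% and 99.7% at the three correlations.

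**The case against.** Five points can be made for the plan.

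1. **Aim 1 is not only about the share.** The overall hypothesis opening the aims section speaks of increased glycolysis driven by mTOR, which can be read as a level, and glycoATP measures that level. The share can also rise purely because mitoATP falls, and glycoATP is needed to see this. This stands. A reader might infer that (i)-(iii) answer a wholly different question from Aim 1; the documents do not support that.
2. **% glycolysis is planned elsewhere.** The hsCRP comparison in Preliminary Data uses the predicted outcome, in children closer to the predicted population. This stands in part. That comparison has no named test, is not carried into Data Analysis, and is not one of (i)-(iii).
3. **The outcome list is not declared exhaustive, and the share follows from the two collected rates.** True. So nothing is lost in data collection, and the gap is one of prespecification. The transformation clause does not close it, because transforming each outcome does not define a ratio of two outcomes.
4. **The sizes are assumed, and the power loss is not universal.** This stands. A reader might infer that rate tests are always weaker. At CV 20%, glycoATP reaches 0.83 when only glycolysis moves and mitoATP 0.96 when only OXPHOS moves. Which test wins depends on a mechanism not known in advance.
5. **Demoting the rates would be a preference.** This stands; naming the share closes the gap without it.

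It can also be said that the Treg proportion is the only outcome that Data Analysis calls primary, and that the study is meant as preliminary data for a grant application. Both limit the consequences but leave the mismatch in place.

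**Conclusion.** The mismatch is in the text and depends on no simulated figure: Aim 1 predicts a percentage, the protocol itself separates percentages from rates, and Data Analysis names only the rates for (i)-(iii). Followed as written, the plan can miss the predicted shift or reject without one.

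How often depends on the baseline share, its SD, the variation in total ATP and the share-total correlation, none of which the documents give. Under the central assumptions the loss is large when total output is unchanged and disappears when one pathway alone moves and variation is low.

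The Treg analysis is unaffected. One limit remains: (i)-(iii) group children by metabolic status, so even with the share added they do not test the inflammation wording of Aim 1 for any outcome. The point should be corrected before analysis; it does not undermine the design.

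**What to change.** In Data Analysis:

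1. Name % glycolysis = 100 × glycoATP/(glycoATP + mitoATP), or log(glycoATP/mitoATP) if the percentage is skewed, as the bioenergetic outcome that tests the Aim 1 prediction in comparisons (i)-(iii).
2. Carry over the hsCRP-quartile comparison of % glycolysis from Preliminary Data, stating the groups and the test, because it is the planned analysis closest to the inflammation wording.
3. Keep glycoATP and mitoATP with estimates and 95% intervals to show which pathway moved. Whether they are also formal tests is the sponsor's choice.

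**Cost.** Wording only: the share comes from the same Seahorse run. The detectable difference cannot be put in percentage points until an SD for the share is available.

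**Multiplicity.** Comparisons (i)-(iii) now carry 3 outcomes × 3 = 9 unadjusted tests. With the share added and the rates kept formal there are 4 × 3 = 12; with the rates supporting, 2 × 3 = 6. The hsCRP comparison is extra in either case. If all tests were independent and no differences existed, the chance of at least one false positive would be 1 − 0.95⁹ = 0.37 now, 1 − 0.95¹² = 0.46 with 12 and 1 − 0.95⁶ = 0.26 with 6. The tests are correlated, and simulation gives lower values of 0.28-0.31 for 9 and 0.23 for 6. The fall to 6 is partly nominal, since 95% intervals on the rates still show which would reach the 5% level.
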